# 3.3 Analysis populations

#### 3.3.1 Complete Case Population

The level of missing data for each outcome will be assessed. If missing outcome data is present the initial analysis will be based on the complete cases as we have allowed 30% for loss to follow-up and non-compliance to GENEActiv monitor. All tests of the effect of treatment on outcomes will be conducted on a complete case (CC) population. That is, all the recruited participants will be included in the analysis, with the exception of those with

missing outcome data. This will be done on a 'by analysis' basis, i.e. only those participants with missing data for variables required for a specific analysis will be removed.

#### 3.3.2 Intention-to-treat Population /Full analysis data

A sensitivity analysis using multiple imputation will be used to impute missing data, to assess the robustness of the conclusions to missing data. This will be a full intention to treat analysis. More detail is in section 5.3.2.2.

#### 3.3.3 Per-protocol Population

Sensitivity analysis will also include a per-protocol analysis. The per protocol (PP) population are those who were compliant with the protocol and have complete data for the analysis concerned on 'by analysis' basis. In the control arm, the PP population will include all participants randomised to that arm with complete outcome data. In the intervention arm, the PP population will be defined as participants who have attended at least one of the two group sessions of the programme i.e. those randomised to intervention but not attending either group session will be excluded and have outcome with complete data. This will be a sensitivity analysis.

# 4 Trial population

### 4.1 Eligibility criteria

Eligibility criteria are described in The BABY STEPS Study Protocol v5; 25/05/2018 7.

### 4.2 Recruitment

A CONSORT chart will summarise the flow of participants through the trial.

### 4.3 Baseline characteristics

Descriptive characteristics at baseline will be summarised by treatment arm. Numbers (with percentages) for binary and categorical variables, and means (and standard deviations) or medians (with lower and upper quartiles) as appropriate for continuous variables will be presented. The number of missing values will be reported in the footnote of the summary table. There will be no tests of statistical significance nor confidence intervals for differences between randomised groups on any of the baseline variables.

# 5 Outcome measures

#### 5.1 Primary outcome measure

The primary outcome measure is change in overall volume of physical activity measured using accelerometer (GENEActiv monitor) between baseline and 12 months.

#### 5.2 Secondary outcome measures

Below is a list of all of the secondary outcomes collected at baseline and follow-up.

#### (i) Ambulatory activity:

Participants will be asked to wear an accelerometer for eight days to record total volume of physical activity, which includes light, moderate, vigorous and moderate to vigorous physical activities (MVPA) and to complete an activity log to provide wear time information. To be included in an analysis a participant needs to provide at least one valid day of accelerometer data.

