# 5.3 Analysis methods

#### 5.3.1 Analysis of primary outcome

The primary outcome is change in overall volume of physical activity (average acceleration, ENMO) from baseline to 12 months. For the primary outcome treatment arm will be compared using linear regression modelling with a binary indicator for randomisation group as the explanatory variable, terms for stratification factors (age and ethnicity) as confounders, and adjustment for the change in accelerometer wear time from baseline and overall volume of physical activity at baseline.

The primary analysis at 12 months will be based on complete data.

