#### 5.3.2.2 Intention-to-treat Population

To allow for full analysis set, missing data will be imputed using a multiple imputation procedure which substitutes predicted values from a regression equation. The imputation will be carried out by the MI command in Stata 15. MI replaces missing values with multiple sets of simulated values to complete the data, performs standard analysis on each completed dataset, and adjusts the obtained parameter estimates for missing-data uncertainty using Rubin's rules to combine estimates.

The following procedure will be followed:

• The MI will be set as wide

• The MI will register imputation of the overall volume of physical activity at 12 months and at baseline

• A regression method will be used , where the registered variables will be individually adjusted for the randomisation and stratification factors (age and ethnicity), with 100 imputations to avoid biased estimates, rseed (2259) and the force options

• MI estimate will provide the final results using the same regression model as the primary analysis and covariate adjustments.

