#### 5.3.2.3 Effects on the number of valid days

Three separate models will be run; including participants who have worn accelerometer for the following:

- At least 2 valid days
- At least 3 valid days
- At least 4 valid days

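### Wear time, a covariate in the primary model, has only a self-completed log as its named source, so a missing log can drop a woman with valid recordings

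*SAP*

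**What the plan says.** Five places in the SAP bear on this.

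- **5.2(i), source of wear time.** Participants wear the device for eight days and are asked "to complete an activity log to provide wear time information". This is the only source of wear time that the SAP names.
- **5.2(i), inclusion.** "To be included in an analysis a participant needs to provide at least one valid day of accelerometer data". The SAP does not define a valid day, and it does not make the log a condition of inclusion.
- **5.3.1, primary model.** The outcome is "change in overall volume of physical activity (average acceleration, ENMO) from baseline to 12 months". The covariates include "adjustment for the change in accelerometer wear time from baseline and overall volume of physical activity at baseline". Wear time is therefore needed at both visits.
- **3.3.1, complete cases.** The population is formed analysis by analysis: "only those participants with missing data for variables required for a specific analysis will be removed".
- **5.3.2.2, multiple imputation.** "The MI will register imputation of the overall volume of physical activity at 12 months and at baseline". Afterwards, "MI estimate will provide the final results using the same regression model as the primary analysis and covariate adjustments". Wear time is not among the registered variables.

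Section 5.3.2.3 adds models that require at least two, three or four valid days. None of them changes where wear time comes from.

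**The concern.** The primary outcome comes from a device, but a covariate needed to analyse it is tied to a form that the participant fills in. This has two possible consequences.

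1. **Loss of women whose outcome was measured.** A woman can have good recordings at both visits and lack a log at one of them. If the log supplies wear time, she has no wear-time change and cannot enter the primary model. The sensitivity analysis that 3.3.2 describes as full intention to treat would not recover her either.
2. **Unrecognised non-wear.** If wear time comes from the log alone, a removal that was not written down has no stated route to being identified as non-wear. Depending on how such time is processed, it could affect average acceleration, the count of valid days and the wear-time covariate.

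Log completion is participant behaviour. In a comparison of an education programme with usual care plus a leaflet, it need not be the same in both arms.

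**Working it through.** **Step 1. Follow a woman with valid recordings at both visits and no log at one of them.**

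- Under the inclusion sentence in 5.2(i) she qualifies, because she has at least one valid day.
- Under 5.3.1 she needs wear time at baseline and at 12 months. If the log is the source, one of the two is missing, and so is the change.
- Under 3.3.1 she is removed, because a required variable is missing. An earlier sentence of 3.3.1 speaks only of missing outcome data. Reading it alone would not save her, since a linear regression cannot use a record with a missing covariate.
- Under 5.3.2.2 only activity volume at the two visits is imputed, and hers is already observed. The refitted model carries the same covariates, so her wear-time change is still missing.

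Sections 5.2(i) and 3.3.1 therefore point in different directions for her, and no rule settles it.

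**Step 2. Reproduce the SAP's sample size (2.3).**

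Inputs: difference 2.1 mg, SD 5.3 mg, power 80%, significance level 5% (all 2.3); two-sided tests (3.1); 1:1 allocation (2.1).

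- Normal approximation: n per arm = 2 × (1.960 + 0.842)² × (5.3/2.1)² = 99.99, so 100 per arm and 200 in total.
- Two-sample t-test: 100.96, so 101 per arm and **202 in total**, as stated.
- Recruitment: 202/(1 − 0.30) = 288.6, so 289, or 290 with equal arms, as stated.

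The sample-size arithmetic stands. The 30% allowance is for loss to follow-up and monitor non-compliance. It names nothing for missing logs.

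**Step 3. Power if missing logs remove evaluable women.**

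The SAP gives no missing-log rate, so the rates below are assumptions. Power is for a two-sample t-test with 2.1 mg and SD 5.3 mg, two-sided 5%. Numbers left are 202 × (1 − rate), rounded down.

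| Assumed share lost | Women left | Power |
|---|---|---|
| 0% | 202 | 80.0% |
| 5% | 191 | 77.8% |
| 10% | 181 | 75.5% |
| 15% | 171 | 73.1% |

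**Step 4. Scale of unrecognised removal, if it were scored as zero.**

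The SAP does not say that it is, so this is conditional. Let M be the mean acceleration that the removed hours would have had, and h the unlogged hours in a day. The 24-hour mean falls by M × h/24. With M assumed to be 25 to 40 mg:

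- One hour on one day lowers that day's mean by 25/24 = 1.04 to 40/24 = 1.67 mg.
- Averaged over eight days of wear, the same single hour lowers the woman's mean by 1.04/8 = 0.13 to 1.67/8 = 0.21 mg.
- To produce a spurious between-arm difference of 2.1 mg, the change from baseline in unlogged removal would have to differ between arms by 2.1 × 24/40 = 1.3 to 2.1 × 24/25 = 2.0 hours on every day.

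**The case against.** The strongest case on the other side is that the SAP is silent and does not prescribe a bad rule. Section 5.2(i) describes what participants are asked to do. It does not say that the log is the only source of wear time or that it overrides the device, and 5.3.1 speaks of accelerometer wear time. The log may only support detection from the signal. Processing detail of this kind may also sit in the protocol, which was not available for this review. The missing-log rates are assumed, and women who skip the log may overlap with the 10% already allowed for monitor non-compliance. The power figures also ignore any precision gained from adjusting for baseline activity. The models in 5.3.2.3 reduce reliance on a single doubtful day.

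Much of this stands, and it makes the loss of women conditional on the log being the source. It does not remove the point. The log is the source the SAP names, the covariate belongs to the SAP's own primary model, and the imputation that should protect against missing data leaves that covariate out. Requiring more valid days does not test where wear time comes from.

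A reader might infer that unlogged removals count as inactivity under this plan. The SAP does not support that. It has no rule for scoring non-wear, so such time could be scored as zero, excluded or replaced. A reader might also set the 1.0 to 1.7 mg shift beside the 2.1 mg target and conclude that the error is as large as the effect. That compares one woman's mean on one day with a between-arm difference in change, and these are different quantities.

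**Conclusion.** The point holds in conditional form. The SAP ties wear time to a self-completed log, uses change in wear time in the primary model, and neither protects nor imputes it. If the log is the source, a missing log at either visit removes a woman whose primary outcome was measured, from both the primary analysis and the imputed one.

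The cost is modest: power falls from about 80% to between 78% and 73% if 5% to 15% of the 202 are lost. Those rates are assumptions, taken to come on top of the 30% allowance.

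Unrecognised non-wear is a possibility, not something the plan lays down. It biases the treatment effect only if the change in unlogged removal differs between arms; otherwise it adds noise. The documents give no basis for estimating its size.

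The change should be made, because a source of wear time that does not depend on the log is available in the recordings themselves.

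**What to change.** In **5.2(i)**:

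- State that wear time, non-wear and valid days at each visit are derived from the accelerometer signal by one pre-specified algorithm, applied masked to arm.
- Define a valid day in those terms, and say how detected non-wear is treated when average acceleration is computed.
- Keep the log only as a check on the algorithm.
- State that a missing log alone does not exclude a participant from any accelerometer analysis.

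In **5.3.2.2**, register wear time in the imputation, so that the refitted model does not drop women for a missing covariate.

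The cost is SAP wording and processing of recordings that the trial collects anyway, with no new visits or data. The downside is that an algorithm may label some very still worn time, such as sleep, as non-wear; the log can help check this. The rule should be fixed before anyone sees results by arm.

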#### (ii) Anthropometric measures:

- Body weight (kg)
- Waist circumference (cm)
- Hip circumference (cm)
- Body Mass Index (kg/m2)

#### (iii) Clinical measures:

- Blood pressure (mmHg)
- Resting heart rate (bpm)
- Total cholesterol (mmol/l)
- HDL cholesterol (mmol/l)
- LDL cholesterol (mmol/l)
- HbA1c (mmol/mol, %)

#### (iv) Questionnaire measures

A number of different questionnaire measures will be completed by participants at baseline and 12 months. Details of these questionnaire measures are as follows:

- Recent Physical Activity Questionnaire (RPAQ) this will assess habitual physical activity in several domains including occupation, leisure, housework
- Health Related quality of life (EQ-5D-5L)
- 5-A-Day Consumption and Evaluation Tool (FACET) this will assess the participants' fruit and vegetable intake.
- Hospital Anxiety and Depression Scale (HADS14) this will assess the severity of symptoms of anxiety and depression.
- Jenkins Self-efficacy for Exercise Expectations Scale this will assess the ability to exercise.

# 5.3 Analysis methods

#### 5.3.1 Analysis of primary outcome

The primary outcome is change in overall volume of physical activity (average acceleration, ENMO) from baseline to 12 months. For the primary outcome treatment arm will be compared using linear regression modelling with a binary indicator for randomisation group as the explanatory variable, terms for stratification factors (age and ethnicity) as confounders, and adjustment for the change in accelerometer wear time from baseline and overall volume of physical activity at baseline.

The primary analysis at 12 months will be based on complete data.

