# 2 Methods

# 2.1 Trial design

The trial is a parallel group randomised controlled trial, in which participants are randomised to two groups (1:1). It will compare a structured education programme plus additional follow on support (a wrist worn activity monitor and interactive web based intervention) with usual care plus an information leaflet. The RCT will be conducted in two centres; University Hospitals of Leicester NHS Trust and George Eliot Hospital NHS Trust. Participants will be followed up for 12 months.

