# 2.2 Randomisation

Randomisation will be stratified by age (<30years; ≥30years) and by ethnicity (White European; other) and participants will be randomised to either the control or the intervention arm.

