# 2.3 Sample size

The primary outcome is based on increasing total physical activity as quantified by the Euclidean norm minus one (ENMO) method measured in milligravity units (mg). This is the

main measure of activity derived from the GENEActiv monitor. In order to detect a minimum clinically significant difference of 2.1 mg, which is equivalent to an overall increase in physical activity volume of approximately 30 minutes of brisk walking at 4km/h, assuming a standard deviation of 5.3 mg , a power of 80% and significance level of 5%, the sample size requires 202 participants. To allow for 20% loss to follow-up and 10% non-compliance of the GENEActiv monitor, we will therefore need to recruit 290 participants (145 in each arm).

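### Centre is in neither the stated strata nor the primary and imputation models of this two-centre trial; adding it is a cheap gain in precision, and its absence does not invalidate the analysis.

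*SAP*

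**What the plan says.** SAP 2.1 states "The RCT will be conducted in two centres" and describes 1:1 allocation to two arms. SAP 2.2 reads "Randomisation will be stratified by age (<30years; ≥30years) and by ethnicity (White European; other"; centre is not named there.

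SAP 5.3.1 sets the primary model as a linear regression on randomised group, with "terms for stratification factors (age and ethnicity) as confounders". The only other covariates it lists are change in wear time and the baseline value of the outcome, so there is no centre term. The imputation step in SAP 5.3.2.2 has each imputed variable "individually adjusted for the randomisation and stratification factors (age and ethnicity", again without centre.

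No other analysis in the SAP brings centre in. The per-protocol analysis (5.3.2.1) repeats the primary steps, the secondary analyses (5.3.3) follow the main one, and centre is not among the subgroups in 5.3.4. No reason for the omission is given.

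**The concern.** Centre is a two-level factor fixed before randomisation and known for every participant. If it is not a stratum, the proportions of women from each hospital can differ between arms by chance. If it is not in the model, the part of any centre difference in 12-month activity that age, ethnicity and baseline activity do not carry stays in the residual. In a particular sample it can then push the treatment estimate up or down.

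The primary analysis uses complete cases, and the sample size allows for 30% without usable data. The analysed set is therefore smaller than the randomised set and can be less balanced by centre. If missingness also depended on centre, the multiple-imputation check would not reflect this, because its model omits centre too.

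At stake are some precision and the ability to answer a question about centre comparability with a term chosen in advance. A centre adjustment introduced after the data are seen is harder to defend.

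**Working it through.** **The plan's own figure.** SAP 2.3 gives a "minimum clinically significant difference of 2.1 mg", SD 5.3 mg, 80% power and 5% significance; 3.1 makes tests two-sided.

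- Normal approximation: 2 × (1.960 + 0.842)² × 5.3² / 2.1² = 100 per arm, 200 in total.
- t-test version: 101 per arm, 202 in total, as stated.
- Inflation: 202 / (1 − 0.30) = 288.6, so 290 as a rounded even total. Conversely, 290 × 0.70 = 203 evaluable.

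The 202 and 290 reproduce.

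**Assumptions, because the SAP gives no figures on centre.** The share at the smaller centre is p = 0.3, with 0.5 for comparison. The residual centre difference after baseline adjustment is d = 0 to 2 mg. The correlation between baseline and 12-month activity is 0.5, so the adjusted residual variance is 5.3² × (1 − 0.5²) = 28.09 × 0.75 = 21.07 mg². Allocation is treated as unrestricted with respect to centre.

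**Size of a chance imbalance.** The SD of the between-arm difference in centre share is √(4p(1−p)/N). With N = 203:

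- p = 0.3: √(0.84/203) = 0.0643; 95% limit 1.96 × 0.0643 = 12.6 percentage points.
- p = 0.5: √(1/203) = 0.0702; 95% limit 13.8 points.

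For a 50:50 split, the chance of a difference of 10 points or more is about 16% at N = 202 and 9% at N = 290.

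**First view: shift in one realised sample.** Shift = imbalance × d. At p = 0.3 and the 95% limit:

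- d = 0: no shift.
- d = 1 mg: 0.126 × 1 = 0.13 mg, 6% of 2.1 mg.
- d = 2 mg: 0.126 × 2 = 0.25 mg, 12% of 2.1 mg.

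**Second view: residual variance.** Added share = p(1−p)d² / 21.07. At p = 0.3:

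- d = 0: 0%.
- d = 1 mg: 0.21 / 21.07 = 1.0%; standard error up by √1.010 − 1 = 0.5%.
- d = 2 mg: 0.84 / 21.07 = 4.0%; standard error up by √1.040 − 1 = 2.0%.

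The share would be larger with a stronger baseline correlation and smaller with a weaker one.

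**The two views are one harm.** Take p = 0.3, d = 2 mg.

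- The SD of the shift is 2 × 0.0643 = 0.129 mg, variance 0.0166.
- With centre in the model, the standard error of the treatment effect is √21.07 × √(4/203) = 0.644 mg, variance 0.415.
- The ratio is 0.0166 / 0.415 = 4.0%, the same 4.0% as above.
- With centre left out, the standard error is √(0.415 + 0.0166) = 0.657 mg. The 95% half-width goes from 1.96 × 0.644 = 1.26 mg to 1.96 × 0.657 = 1.29 mg.

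**Power.** Treat 5.3 mg as including centre variation and, as in SAP 2.3, ignore baseline adjustment. With 101 per arm and p = 0.3, adding centre raises normal-approximation power from 80.4% to 80.7% (d = 1 mg) or 81.7% (d = 2.1 mg).

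**The case against.** The best defence is that the plan is coherent. The model adjusts for exactly the factors named as strata and for the baseline value of the outcome, which is an ordinary choice. Nothing is contradicted. Leaving out a factor that was not stratified on could equally be criticised for parity or BMI. This stands in part: there is no internal contradiction. Centre differs from those covariates in being a structural feature of the design.

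A reader might infer that the omission biases the primary result. The documents do not support that. Allocation is random, so the estimate is unbiased on average, and the standard error from the planned model already covers chance centre imbalance. Type I error and interval coverage hold. A reader might also count the shifted estimate and the larger variance as two separate harms; the working shows that they are the same quantity.

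The size is also open to challenge. A residual difference of 1 to 2 mg is about half to nearly all of the 2.1 mg target, after adjustment for the variables through which the two hospitals' populations would mostly differ. Nothing in the SAP supports such a value, and zero is just as compatible with it. Even at 2 mg, the 95%-limit shift is 0.25 / 0.644 = 0.39 of a standard error, and a typical (1 SD) shift is 0.2. This stands, and is why the range starts at zero.

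Finally, SAP 2.2 is a single-sentence summary. Whether lists were generated separately by site may be set out in the protocol, which was not available. The text supports saying only that centre is not a stated stratum; it does not establish that allocation was unbalanced within centre.

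**Conclusion.** The point holds as a minor improvement. Centre is absent from the stated strata, from the primary model and from the imputation model, and the SAP itself fixes those covariate lists. The cost is a small loss of precision and the lack of a direct correction for a chance centre imbalance. The validity of the primary analysis is not in question.

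At an assumed 70:30 split and baseline correlation of 0.5, a residual centre difference of 0 to 2 mg makes the standard error 0% to 2% larger. The equivalent single-sample statement is a shift of at most about 0.25 mg at the 95% limit of imbalance. If the centres do not differ, nothing is gained by adjusting. If allocation was in fact balanced within site, the imbalance part largely falls away and the case for the term rests on residual variance.

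**What to change.** In SAP 5.3.1, add a two-level centre indicator as a fixed effect in the primary linear model. In 5.3.2.2, add the same term to the imputation model: the final imputed analysis reuses the primary regression, so the imputation step should contain every factor that regression contains. The per-protocol analysis inherits the change because it follows the primary steps.

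The point does not require centre in every secondary model. In the logistic and ordinal models of 5.3.3 an added covariate changes the conditional odds ratio being estimated, so whether the term carries over there is a separate choice. Because 5.3.3 says those analyses resemble the main one, a short sentence should state which applies.

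The cost is one phrase in each of two sections and one degree of freedom in about 200. The 202 evaluable and 290 recruited participants are unaffected. The change should be made before the analysis is run.
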